2.1 Design / Approach

This investigation is a mixed methods study comprising:

- (i) Digital health participation scale development and validation via a scoping review of extant measures and focus groups and workshops with people with intellectual disabilities and carers (WP1);
- (ii) Longitudinal survey to: (a) identify levels of digital health participation; (b) determine changes over time and identify causal relationships between aspects of digital health participation and wellbeing, utilising a cross-lagged path analysis, while controlling for demographic and background characteristics; and (c) determine levels of digital health inequality of people with intellectual disabilities compared with a non-disabled referent group (WP2);
- (iii) Digital diary study utilising ArcGIS storytelling software to explore the challenges, facilitators and experiences of digital health participation.
- (iv) Co-creation of resources to better support the digital health participation of people with intellectual disabilities and their carers.

This study will adopt a nuanced approach to digital health participation incorporating: (i) a strengths based approach, drawing on self-determination theory, to discern the skills, independence, and supports pertaining to successful digital health participation (Niemic *et al.*, 2017; Wehmeyer 2020a, 2020b); (ii) a digital participation framework, including ICT use, access and digital participation; and (iii) a health literacy framework, assessment of which includes access to health information, functional appraisal skills, communicative and social influences and critical health decision making (Chinn, 2014) and should involve people with intellectual disabilities (Chinn, 2014; Geukes *et al.*, 2018; Latteck & Bruland, 2020).

A logic Model for the proposed study is presented in Appendix 1.

The project will be delivered over 32 months across 4 study sites (East Central Scotland – DU; North West England – LJMU & MMU; South East England – UoK; West Midlands England – LJMU). With 3 months for project set up, 8 months for WP1, 19 months for WP2, 12 months for WP3 and 13 months for WP4 with overlapping work across 4 sites for WPs 2, 3 and 4. A detailed project plan (Appendix 2), and a summary of key timelines and milestones is provided: Set-up of management and steering groups (m1-3) and staff recruitment (m1-3 and m9-11); WP1 Survey Development (m4-11); WP2 Longitudinal survey (m11-30); WP3 Digital Diary Study (m14-27); WP4 Dissemination & Output Co-creation (m14-16 and 24-32). A schedule of procedures is presented in Appendix 3.

2.2 Project Set up (Months 1-3)

Preliminary and start up tasks will be carried out in the first 3 months of the project. These include the following tasks:

Task 1. Preparation of Ethical Approval and Study Documentation

Task 2. Recruit research associates/fellows (RA) and co-researchers (CR) with intellectual disabilities

Task 3. Provide preliminary project training to RAs and CRs

Task 4. Set up 4 monthly project steering committee (comprising representation from key stakeholder groups: people with intellectual disabilities, staff and family carers, healthcare providers and professionals, digital content providers).

Task 5. Set up monthly management group (comprising the chief and co-investigators and RAs).

2.3 Development of the Digital Health Participation Measure (Months 4-11) - Work Package 1 (WP1).

2.3.1 Scale Development Process

A validated assessment of digital health participation will be developed. This will incorporate recommended stages of scale development (Kooijmans *et al.*, 2022): (i) item generation (via a review of pre-existing scales of digital participation and health literacy and focus groups with people with intellectual disabilities and carers); (ii) creation of the content incorporating adaptations (Kooijmans *et al.*, 2022) to language, response formats and supportive media layouts (enabled by pictorial representations of key aspects of digital health participation

drawn by an illustrator working alongside the co-researcher with intellectual disabilities); (iii) piloting the draft-seeking consensus from people with intellectual disabilities, carers and professional experts; and (iv) psychometric analysis.

2.3.2 Item Identification & Selection

Two parallel processes will be undertaken: (i) a full review of the extant literature and broader practice-based resources and (ii) a series of focus groups with key stakeholder groups.

Review of the literature – Search Strategy

A full review of the literature (Heyvaert et al., 2016) will be conducted to gather existing measures of: ICT use and access (Chadwick *et al.*, 2022); digital literacy; online support; functional, interactional and critical health literacy (Chinn, 2014); and online health activity, access and use. Key words will be generated pertaining to these components of digital health participation for the review. Use of databases (CINHAL, Psychinfo, Medline), hand-searching of references, and communication with authors will all be utilised in the review. Keywords will be adapted for use with each database. In addition, we will put out a call to online networks of service providers and those interested in digital inclusion of people with disabilities to gather existing practice measures.

Studies will be identified via an initial title and abstract screening conducted by the RA and CI. Paper will be included for full screen if they address or incorporate conceptualisations salient to digital health participation and if they have developed or utilised a measure relevant to digital health participation. The search will consider both literature focusing on people with intellectual disabilities and measures and conceptualisations from the broader literature.

Papers included following full screening will be categorised into conceptual papers, empirical papers investigating qualitative and quantitative aspects of digital health participation and papers developing or using existing measures of key concepts detailed above. Conceptual and empirical articles will be tabulated and synthesised into core aspects of digital health participation using thematic analysis (Heyvaert *et al.*, 2016). The psychometric quality (reliability, validity, factor structure) of pre-existing gathered measures will be tabulated and used to inform decision making regarding item inclusion. Full versions of literature and

practice-based measures will be gathered and items will be thematically analysed and grouped conceptually in readiness for scale construction.

A preliminary search of MEDLINE, the Cochrane Database of Systematic Reviews and JBI Evidence Synthesis has been conducted and no current or underway systematic reviews or scoping reviews on the topic of measurement of digital health participation in people with intellectual disabilities have been identified.

Focus Groups with Key Stakeholders

Adults with a diagnosis of intellectual disabilities, their families and paid carers (as proxy participants for people with higher support needs) are the target participant populations. For WP1 focus groups will be conducted at a single time point for each participant at the site University or partner organisation.

Eight focus group meetings with 4-6 people with intellectual disabilities (N=40) and 4 focus groups with 4-6 (N=20) carers, equally split across the four study sites, will be conducted. Data gathered will be analysed inductively to identify digital health participation skills, support processes and contextual influences not considered within existing scales. This equates to a moderately large sample for a qualitative study (Clarke & Braun, 2013). Recruitment into the focus groups will be facilitated by our partner organisations and Birmingham Community Health Care NHS Foundation Trust and maximum variation sampling to provide a breadth of experiences of digital health participation will be employed. Our overall planned accrual rate is 10 participants per month over six months to reach our aim of a final sample size of up to 60.

Participants in these workshops will be offered the opportunity to return for the digital health participation measure co-creation workshops.

2.3.3 Data synthesis and analysis

Items from prior scales and focus group data will be collated and analysed using thematic framework analysis (Gale *et al.*, 2013) to identify key components of digital health participation for people with intellectual disabilities and generate accessible items to assess them. Trustworthiness strategies will be embedded in the qualitative analyses for both WP1 and WP3 (Amankwaa, 2016; Shenton 2004), along with dialogue and checks conducted with research partners (Nyirenda *et al.*, 2020).

2.3.4 Scale Construction

Preliminary scale items will be shared in two co-creation workshops, one with people with intellectual disabilities and another with carers, to develop and work towards reaching consensus (Kooijmans *et al.*, 2022). From these, a long list of items will be generated for the Digital Health Participation Survey (self/supported completion) and Carer Proxy Digital Health Participation Survey. Items in these two measures will mirror each other with the latter containing third person rather than first person text. This measure of digital health participation will comprise: (i) Digital participation: access and use; skills and literacy; self-efficacy; (ii) Support for digital participation; (iii) Health literacy: functional; interactional; critical decision-making; (iv) Frequency and success of engagement in digital health activity (e.g. information seeking, video-consultation, health appointment and communications, use of digital health monitoring devices); (v) Additional inductively derived aspects of digital health participation which do not readily fit with the utilised frameworks. Piloting of the survey will occur with focus group participants prior to roll out in WP2.

A manual for the finalised scales will be developed. This will detail administration for people with intellectual disabilities from independent self-completion, through differing levels of support needs through to full proxy completion for participants with higher support needs, for example, those who are minimally verbal or have profound intellectual and multiple disabilities. Guidance on decision making regarding whether independent, supported or proxy completion is most appropriate will be included within the manual. This decision will be based on level of support needs, literacy, information processing and comprehension considerations. This will enable the measure to be applicable to all people with intellectual disabilities addressing the considerable heterogeneity within this population.

In addition, filtered administration logic will be developed, whereby initial screening by particular overarching questions can remove the need to subsequently answer sub-questions. This will both to reduce participant burden and administration time.

2.3.5 Psychometric Analyses

Validation via exploratory and confirmatory factor analyses and reliability analysis will occur concurrent to WP2 following steps 5 to 9 in Boateng *et al.* (2018), who also suggest a sample size between N=200-450 is sufficient for psychometric analysis. The analyses will assess items and the underlying factor structures among them. On this basis, some items

may be refined or removed. Confirmatory factor analysis will be used to determine if the hypothesised underlying structure of items is captured by the items (Wang & Wang, 2012). If the hypothesised structure does not provide sufficient model fit, models with different numbers of factors will be compared using likelihood ratio tests (specifically, using AIC and BIC criterion) to establish the most appropriate structure. All models will be reported with robust standard errors and model fit will be evaluated using the comparative fit index (CFI >0.9), Tucker-Lewis Index (TLI >0.9), standard root mean squared residual (SRMR <0.08) and root mean square error of approximation (RMSEA <0.08), (see Wang & Wang, 2012; Hu & Bentler, 1999; Schreiber *et al.*, 2006). We will report the internal consistency of items in the measure using McDonald's Omega (Andrew *et al.*, 2020).

2.4 Longitudinal Digital health Participation Survey Study (Months 11-30) and Comparative Study of Digital Health Inequality (Months 11 to 22) - Work Package 2 (WP2).

In this work package we will conduct two inter-linked investigations: A longitudinal survey study to identify factors influencing the digital health participation and wellbeing of people with intellectual disabilities and a comparative study contrasting levels of digital health participation between people with intellectual disabilities and a referent group of non-disabled people.

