2.4.1 Longitudinal Survey Study

The digital participation survey (Proxy or Self/supported completion as appropriate) will be administered to a convenience sample of 400 people with intellectual disabilities at two time points eight months apart (+/-1 month). This sample size will enable digital health participation for people with intellectual disabilities to be adequately understood across the breadth and heterogeneity inherent in this population. It will also enable a sufficiently powered analysis to identify moderate effect sizes in relation to predictors of digital health participation.

Survey sampling & recruitment

Adults with a diagnosis of intellectual disabilities and the family and paid carers (as proxy participants for people with higher support needs) are the target population. Taking a whole population approach, and to increase geographical diversity, a self-selecting sample of 400 adults with intellectual disabilities will be recruited equally from the four study sites.

Recruitment will be facilitated by partner organisations with established groups of people with intellectual disabilities and links with additional community groups and agencies which contain under-represented groups of people with intellectual disabilities. Birmingham Community Healthcare NHS Foundation Trust will also act as a recruitment centre. Our overall planned accrual rate is 50-60 participants per month across the four study sites (12-15 per site) over seven months to reach our aim of a final sample size of 400 (Note we expect some of the 60 participants from WP1 to participate in WP2 and WP3).

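### A factor structure reached by dropping items or re-selecting the number of factors in WP2 is judged on the same respondents, so its fit is exploratory and does not validate the scale

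*Protocol*

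**What the plan says.** Protocol section 2.3.5 sets the timing: "Validation via exploratory and confirmatory factor analyses and reliability analysis will occur concurrent to WP2". The sample-size basis is a cited rule, that "a sample size between N=200-450 is sufficient for psychometric analysis". On the results, some items "may be refined or removed".

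The first use of CFA is a test of a structure fixed in advance: "Confirmatory factor analysis will be used to determine if the hypothesised underlying structure of items is captured by the items". If that fit is not good enough, "models with different numbers of factors will be compared using likelihood ratio tests". All models are then held to the same limits: CFI and TLI above 0.9, SRMR and RMSEA below 0.08.

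Before WP2 the survey is only piloted, with focus-group participants (section 2.3.4). Section 2.4.1 gives the survey to 400 people with intellectual disabilities twice, eight months apart, and adds that "we expect some of the 60 participants from WP1 to participate in WP2 and WP3". Section 2.4.2 makes the resulting score the primary outcome of the group comparison and defers a more detailed SAP until WP1 is complete. Objectives iii and xi (section 1.4.2) promise a psychometrically valid measure.

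**The concern.** WP2 is the only administration to people with intellectual disabilities large enough for factor analysis. The referent group of 200 also completes the survey but is a different population. Exploration, item removal, CFA and the fallback therefore all draw on one set of respondents. Once items have been dropped or the number of factors re-chosen because of how those respondents answered, good fit in them partly reflects the choosing. Repeating the CFA at wave 2 does not cure this, because the people are the same.

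The validity claim is at stake: passing the cut-offs by this route would be reported as validation when it is exploratory.

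A second, smaller matter is timing. A removed item can be left out of scoring afterwards. A reworded item cannot be applied to answers already collected. Refinement concurrent with WP2 therefore leaves room for the administered form to change during fieldwork, and no passage says that the items are held fixed.

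**Working it through.** **The plan's own figure.** The psychometric range of 200-450 is cited and has no inputs to reproduce. The nearest calculated figure is the power of the comparison that uses this score (section 2.4.2: 400 vs 200, d = 0.2812, α = 0.05). Taking α as two-sided, d × √(200 × 400 / 600) = 0.2812 × 11.547 = 3.247, and 3.247 − 1.960 = 1.287, which gives power 0.901 (0.900 by noncentral t). The stated 90% reproduces and is not in question.

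**Which routes are confirmatory.**
- Pre-specified structure, all items, tested first: confirmatory, even in the full 400.
- CFA after items are removed on the same records: exploratory.
- Structure from the fallback re-selection on the same records: exploratory.
- Selection at wave 1 and CFA at wave 2: same people, so not independent.

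**Room for a split.**
- Wave 1 of 400: 400 / 2 = 200 per half, the bottom of the protocol's range.
- Wave 1 oversampled for 15% loss: 400 / 0.85 ≈ 471, about 235 per half.
- Wave 2 after 15% loss from 400: 400 × 0.85 = 340, so 170 per half, below the range.

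A split should therefore be made at wave 1.

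**Size of the optimism (illustrative, on assumed populations).** The first simulation had 24 items, three factors and minor nuisance factors. Items were dropped on exploratory loadings, over 300 runs. SRMR and re-selection of the number of factors were not simulated.

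| Data | Mean CFI | CFI, TLI and RMSEA limits all met |
|---|---|---|
| N=400, same data | 0.889 | 17% |
| N=400, new sample | 0.885 | 14% |
| N=200, same half | 0.892 | 27% |
| N=200, hold-out half | 0.879 | 20% |

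The gaps in CFI are 0.889 − 0.885 = 0.004 and 0.892 − 0.879 = 0.013. A second simulation pruned harder, from 24 to 15 items by largest CFA residuals at N=400, with only 60 and 25 replicates. It gave 0.960 vs 0.936 and, in a noisier population, 0.848 vs 0.808, gaps of 0.024 and 0.040. The protocol does not describe that pruning rule. The direction agrees throughout; the size depends on the assumptions.

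**Timing.** Assume recruitment starts in month 11. Seven months of accrual ends wave 1 near month 18. Wave 2, 8 ± 1 months later, runs from about 11 + 7 = 18 to 18 + 9 = 27. Item decisions taken during WP2 could therefore fall between the waves.

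**WP1 overlap.** At most 60 / 400 = 15% of respondents helped shape the items. This is a ceiling: the text says only some, and 20 of the 60 are carers (section 2.3.2).

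**The case against.** The strongest reply is that the protocol nowhere says exploratory and confirmatory analyses use the same records. A random split is compatible with section 2.3.5, the cited scale-development guide may address it, and allocating records is ordinary SAP content. That stands in part: silence is not a plan to reuse data. But the protocol itself fixes a sequence of pruning and fallback re-selection, and applies one set of cut-offs to every model without separating the confirmatory result from the exploratory one. Keeping the administered form fixed is a data-collection rule and should not wait for an analysis plan.

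Four stronger readings are tempting and are not supported:
- **That no CFA here can be confirmatory.** The components are listed in advance (section 2.3.4) and the fallback is conditional, so a first test on all items would be a proper one.
- **That the scale will differ between waves.** Section 2.4.1 and the plain English summary describe one survey given twice. The logic model in Appendix 1 separates an initial survey for WP2 from a final one released in WP4. The natural reading is one form administered twice and pruned later.
- **That the optimism is enough to carry a failing scale over CFI 0.90.** In every simulated scenario both mean values lie on the same side of 0.90.
- **That item pruning biases the group comparison or the cross-lagged paths.** Pruning works on item covariances, not on those contrasts, and no bias has been shown.

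**Conclusion.** The point holds for any structure reached after item removal or through the fallback: its fit is exploratory, and meeting the CFI, TLI, SRMR and RMSEA limits does not validate the scale. It does not hold for a first CFA of the pre-specified structure on all items. The numerical effect is probably modest at N=400 (0.004 in CFI in one simulation, 0.024 to 0.040 under harsher pruning), and all of these values rest on assumed populations. The case therefore rests on how the result is labelled, not on a particular size of bias. A change of form during fieldwork is permitted by the wording but not planned. The point should be settled before the WP2 data are analysed; it does not undermine the design.

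**What to change.** 1. Test the pre-specified structure first, on all items.
2. If items are then removed or the number of factors is re-selected, do so in one random half of wave 1 (about 200), stratified by site and by WP1 participation. Report CFA fit and omega in the other half (about 200). Alternatively, use all 400 and label the re-selected structure and its fit as exploratory.
3. Do not put all WP1 participants in the selection half: up to 60 / 200 = 30% there against none in the other would make the halves non-exchangeable.
4. Keep administered items and wording identical from the first wave 1 to the last wave 2 completion, and in the referent group.
5. Apply removals to scoring only, identically at both waves and in both groups. Hold wording refinements for the final WP4 version.
6. Lock the scoring before the group comparison and the cross-lagged analysis are run.

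The cost is wording in the protocol and SAP, with no extra participants. The split halves sit at the bottom of the protocol's own 200-450 range, so loadings are less precise. The unsplit alternative keeps precision but gives up the claim of confirmation for any revised structure.

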2.4.1 Longitudinal Survey Study

The digital participation survey (Proxy or Self/supported completion as appropriate) will be administered to a convenience sample of 400 people with intellectual disabilities at two time points eight months apart (+/-1 month). This sample size will enable digital health participation for people with intellectual disabilities to be adequately understood across the breadth and heterogeneity inherent in this population. It will also enable a sufficiently powered analysis to identify moderate effect sizes in relation to predictors of digital health participation.

Survey sampling & recruitment

Adults with a diagnosis of intellectual disabilities and the family and paid carers (as proxy participants for people with higher support needs) are the target population. Taking a whole population approach, and to increase geographical diversity, a self-selecting sample of 400 adults with intellectual disabilities will be recruited equally from the four study sites.

Recruitment will be facilitated by partner organisations with established groups of people with intellectual disabilities and links with additional community groups and agencies which contain under-represented groups of people with intellectual disabilities. Birmingham Community Healthcare NHS Foundation Trust will also act as a recruitment centre. Our overall planned accrual rate is 50-60 participants per month across the four study sites (12-15 per site) over seven months to reach our aim of a final sample size of 400 (Note we expect some of the 60 participants from WP1 to participate in WP2 and WP3).

Partner organisations will ensure adequate oversampling to offset participant drop out. The organisations will also support sample replenishment in the case of non-completion of the survey at time 1. Levels of dropout in longitudinal studies with individuals with intellectual disabilities is approximated at 13% (McCarron *et al.*, 2020); however, we will conservatively allow for up to 15% via oversampling (McCarron *et al.*, 2020). To ensure inclusion of under-represented groups (e.g. people with intellectual disabilities from: ethnic minority/global majority groups, with autism, who are older, and who have underlying physical health problems) and groups more at risk of digital exclusion (older; unemployed; living in group settings supported by paid staff; people with greater support needs (via carers) (Anrijs *et al.*, 2022), sample characteristics will be reviewed after 25% of initial survey data collection has been achieved. If insufficient at initial recruitment, a purposive/targeted sampling strategy, facilitated by partner organisations, will be implemented to ensure adequacy of representation. This review process will be repeated once 75% of initial survey data collection is complete.

Longitudinal survey data collection

Prior to data collection, participants and their carers will be invited to attend online training workshops provided within the project to support the survey data collection (Work package 2). Training will be provided by the CI and site/regional PIs alongside the RAs and the CRs with intellectual disabilities.

Participants will choose their preferred modality for survey completion (Paper-based, online completion (housed on Qualtrics), telephone completion, face-to-face completion as an interview with the geographically closest researcher or a known carer). Where appropriate, the survey will be administered by RAs and CR at each study site. Self and carer supported completion will also be offered for data collection. Survey methods are viable for use with people with intellectual disabilities and have been used successfully by applicants previously and in recent large-scale studies (e.g. Caton *et al.*, 2022). Guidance on completion will be

provided in the manual with individualised support offered by RAs and co-researchers on an as needed/requested basis. The manual will provide guidance on deciding whether independent completion, supported completion or, proxy completion is most appropriate. The survey digitally housed (Qualtrics), printed versions of the survey will also be available if requested for subsequent entry by RAs. Carers proxy completing the survey will also be offered the same range of completion options (Paper-based, online completion (housed on Qualtrics), telephone completion, face-to-face completion as an interview with a researcher).

The survey will comprise: (i) The Digital Health Participation Survey developed in WP1; (ii) General ICT Use and Access (Anrijs *et al.*, 2022); (iii) Physical and Mental Wellbeing (EQ-5-3L, (Herdman *et al.*, 2011)); (iv) Salient Demographic (Gathered from participants in accordance with PROGRESS-plus criteria) (Oliver *et al.*, 2008; O'Neill *et al.*, 2014) and Background information (Current and historical health conditions, ongoing health involvement, day activities, levels of support need, literacy and communication, level of cognitive impairment and postcode to enable gathering of deprivation indices).

Longitudinal survey statistical analysis

Descriptive analysis of levels and frequency of digital health participation. A cross-lagged path analysis (CLPM) will investigate changes over time and identify causal relationships between aspects of digital health participation and physical and mental wellbeing, while controlling for demographic and background characteristics (Kenny & Harackiewicz, 1979). By fitting the model with causal crossed lagged pathways in both directions, we can address whether aspects of digital health participation causally precedes physical and mental wellbeing or vice versa in individuals with intellectual disabilities. Sample sizes $N=100 - 400$ are sufficient for structural equation modelling; more specifically, $N=150$ for models including seven or fewer variables with modest communalities (below 0.5) and zero under identified constructs (Hair *et al.*, 2014). We will fit models with and without cross lagged effects and use likelihood ratio tests (specifically, AIC and BIC criterion) to compare these nested models to determine which better fits the data (Kenny & Harackiewicz, 1979). If data is found to be missing at random (MAR), CLPM analyses will default to using full-information maximum likelihood. All models will be reported with robust standard errors and model fit will be evaluated using the comparative fit index (CFI >0.9), Tucker-Lewis Index (TLI >0.9), standard root mean squared residual (SRMR <0.08) and root mean square error of approximation (RMSEA <0.08), (see Wang & Wang, 2012; Hu & Bentler, 1999; Schreiber *et al.*, 2006).

